## **Aims, purpose, or objectives:**

### **Primary Objective**

1. The primary objective is to demonstrate whether a vascular boot warming program plus standard anticoagulation over standard anticoagulation can improve resolution of DVT±PE and functional performance in patients with deep vein thrombosis of the lower extremity ± pulmonary embolism.

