*Target accrual is the proposed number of subjects to be included in your study at your site. “Subjects” may include Mayo Clinic charts, records, or specimens, **and/or** charts, records, or specimens received at Mayo Clinic from external sources for collaborating analysis by the investigator under this IRB application:*

**Target accrual:** 30 patients (15 patients with vascular boot vs 15 patients without vascular boot)

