**Study Procedure**

All subjects included in this study will have a diagnosis of deep vein thrombosis that will undergo standard anticoagulation with or without wearing a vascular boot. Medical charts will be abstracted for clinical, laboratory, medications, imaging and pathologic findings. Subjects will undergo their initial (baseline) clinically indicated DVT ultrasound for diagnosis of lower extremity DVT. The second clinically indicated limited venous ultrasound will be completed on post-DVT day 90 (14±days) to evaluate resolution. Research ultrasound intervals will then occur on days 0 (+1 days), 3 (-2/+5 days), 10 (±5 days), and 90 (14±days). Shear wave elastography will be conducted at all post-treatment ultrasound intervals. We will compare the shear wave elastography to the opposite lower extremity veins on the same individual for a control if DVT is not present in that extremity at that time or previously.

Commercially available ultrasound systems (Logiq E9, GE Medical Systems, Milwaukee, WI, USA) equipped with phased-array and linear transducers will be utilized. Longitudinal and short axis images of each clot will be acquired and digitally stored for offline analysis. The short axis images will be acquired. 2-D images, 2D shear wave and elastography images will be acquired and digitally stored for off-line analysis. All measurements will be made in a blinded fashion by a single observer.

**Shear Wave Elastography:** The subject will be asked to lay on a hospital bed for ultrasound imaging. The veins of the lower extremity will be visualized using ultrasound imaging, and the depth of the venous wall will be noted. The focal depth on the device will be set to measure shear wave propagation in the walls of the vein and in the thrombus. Measurements will be made at multiple locations along the veins length.

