**Statistical Considerations**

**Data Analysis Plan:**

This is a pilot study including 30 volunteers. Sample size cannot be calculated statistically due to lack of prior studies in the literature for those with DVT and use of warming boot. We will recruit up to 30 subjects who have valid measurements as described in the Data Analysis plan.

The ultrasound measurements (elastography) will be assessed for validity using data analysis techniques and to examine the visualization of the venous wall to see if we can quantify the thrombosis.

All statistical tests will be 2-tailed at a significance level of  $P < 0.05$ . Demographic and physical characteristics laboratory values and comorbid conditions will be presented as mean  $\pm$  standard deviation for continuous variables and as frequencies and percentages for categorical variables. Counts and percentages will be presented for categorical variables, while means  $\pm$  standard deviations and 95% confidence intervals will describe continuous variables for which normality assumptions are met. If the distribution of a continuous parameter is skewed, transformations will be considered, or medians and interquartile ranges (IQR) will be presented. Continuous variables will be compared between 2 groups using unpaired t-tests. For comparison of continuous variables in  $\geq 3$  groups, one-way analysis of variance (ANOVA) followed by a Scheffé test may be performed. Frequencies will be compared using Chi square analysis. The correlation between 2 continuous variables will be determined using a linear regression analysis. Cox proportional hazards regression will be used to estimate the

association between thrombosis and short-term and long-term outcomes. Logistic regression will be used to estimate the association between thrombosis and binary outcomes. Adjustment for potential confounders will be accomplished through, either, covariance regression modeling, propensity score stratification, or propensity matching, according to the discretion of the statistical analyst. Statistical analyses will be performed using SAS and/or R software.

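### The plan lets the analyst choose the adjustment method, propensity matching included, and does not exclude the randomised SOC v VB comparison from that choice

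*Combined protocol and SAP*

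**What the plan says.** The Primary Objective is to "demonstrate whether a vascular boot warming program plus standard anticoagulation over standard anticoagulation can improve resolution" of the clot, and functional performance. Target accrual is 30, split 15 with the boot and 15 without. The Methods randomise patients through REDCap after the baseline studies.

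The Data Analysis Plan, under Statistical Considerations, then gives these analyses:

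- **Two-group tests.** "Continuous variables will be compared between 2 groups using unpaired t-tests", and "Frequencies will be compared using Chi square analysis". The groups are not named.
- **Cox model.** It estimates the "association between thrombosis and short-term and long-term outcomes".
- **Logistic model.** "Logistic regression will be used to estimate the association between thrombosis and binary outcomes".
- **Adjustment.** Potential confounders are handled by covariance regression modelling, "propensity score stratification, or propensity matching, according to the discretion of the statistical analyst". No covariates, caliper or matching rule are given.

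Under Study Procedure, "All subjects included in this study will have a diagnosis of deep vein thrombosis".

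**The concern.** The question the trial was set up to answer is SOC v VB. The two regression models do not mention arm, and the tests that probably do compare the arms are not labelled as doing so. The adjustment sentence comes straight after the thrombosis models and may be meant only for them, but nothing limits it to them.

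If the sentence were applied to the arms, three things would follow:

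- Propensity methods exist to repair non-random assignment. Here assignment is random, so only chance imbalance is left.
- Matching with a caliper would discard patients from a trial of 30.
- An analyst who may pick among three methods after seeing the data can report the most favourable one, and the plan does test at a two-sided 5% level.

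There is also a missed gain. Plethysmography is measured at baseline and at 3 months, yet the named test for it is an unpaired t-test, which ignores the baseline value.

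**Working it through.** **1. Reading the text.** The plan has no sample size calculation to reproduce; the only arithmetic is 15 + 15 = 30, which agrees with the pilot size in the Data Analysis Plan. Going through the listed analyses for one tied to the randomised arm:

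| Analysis | Term or groups named | Arm named? |
|---|---|---|
| Unpaired t-test | 2 groups | No, but SOC and VB are the only treatment groups defined |
| Chi-square | Frequencies | No; same remark |
| Cox | Thrombosis | No |
| Logistic | Thrombosis | No |
| Adjustment | Potential confounders | No; not limited to any analysis |

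**2. What matching would do if applied to the arms.** Assumptions, none from the plan: 15 per arm, 1, 2 or 4 baseline covariates, a logit propensity score, greedy 1:1 matching, 4,000 simulated trials per setting. Share discarded = 1 − pairs/15.

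| Caliper (SD of logit score) | Mean pairs kept (1 / 2 / 4 covariates) | Discarded |
|---|---|---|
| 0.1 | 6.49 / 6.40 / 6.03 | 57-60% |
| 0.2 | 8.81 / 8.62 / 8.05 | 41-46% |
| 0.5 | 11.47 / 11.04 / 10.16 | 24-32% |
| None | 15 / 15 / 15 | 0% |

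For example, 1 − 8.81/15 = 0.413 and 1 − 8.05/15 = 0.463.

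Without a caliper, all 15 pairs form. The mean of the pair differences is then (sum of VB outcomes − sum of SOC outcomes)/15, which is the unadjusted arm difference. Matching leaves the estimate as it was.

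For a continuous outcome, the matched 95% CI half-width ran from 0.74 to 1.12 SD at the 0.2-SD caliper and from 0.91 to 1.38 SD at 0.1 SD, against 0.74 SD unadjusted. At 0.2 SD the loss of precision therefore ranges from none to substantial.

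**3. What free choice would do at worst.** If all three methods were run on the arms and the smallest p-value reported, type I error was 7-11% (1 to 4 covariates explaining 0 to 50% of outcome variance, 0.2-SD caliper). A separate run with 3 or 5 covariates gave 8-9%, while each method used alone stayed between 2.3% and 5.6%.

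**4. What one prespecified regression would do.** Unadjusted, with SD 1: half-width = t(0.975, 28 df) × √(2/15) = 2.048 × 0.365 = 0.748. With the SD estimated from the data, the simulated median is 0.739. Regression on arm plus baseline scales as roughly 0.752 × √(1 − r²), where r is the baseline-outcome correlation (assumed; the plan gives none):

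| r | Median half-width (SD) | Change from 0.739 | Power at 1 SD |
|---|---|---|---|
| 0 | 0.752 | +2% | 73% |
| 0.3 | 0.718 | −3% | 78% |
| 0.5 | 0.653 | −12% | 85% (84.5) |
| 0.7 | 0.537 | −27% | 95% |

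The t-test has about 75% power at 1 SD throughout. The two half-widths are equal where √(1 − r²) = 0.739/0.752 = 0.983, that is r of about 0.19. Above that, the regression is the more precise.

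**The case against.** The case against has real force, and much of it stands.

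- **Arm comparison.** A reader might infer that the plan has none. It does not go that far: SOC and VB are the only treatment groups the protocol defines, so the two-group tests most naturally mean those arms. What is missing there is a label.
- **Thrombosis as exposure.** A reader might infer that the Cox and logistic models cannot be fitted, because every subject has a clot. That holds only if the word means presence of thrombosis. The same section speaks of quantifying the thrombosis, and Table 2 grades it by segment, so extent is the likelier meaning, and extent varies. The term is undefined, but the models are not shown to be inestimable. Even so read, they do not test the boot.
- **Loss of patients.** A reader might infer that the plan will discard patients. That needs the clause to be applied to the arms, matching to be chosen and a caliper to be used. The plan states none of these.
- **Selective reporting.** The plan offers the methods as alternatives and does not say that all will be run. The 7-11% is a worst case.
- **Regression is already allowed.** Covariance regression is the first option listed and is close to what is recommended here. The difference is that it would be fixed in advance and the other two removed.
- **Pilot status.** The template note excuses power analyses and endpoints. That limits the consequence, but it does not cover an open choice of method in a plan that tests at 5%.

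**Conclusion.** The concern holds in a limited form. The plan leaves the adjustment method to the analyst and does not keep propensity stratification or matching out of a randomised 15:15 comparison, where they have no selection problem to solve. It also sets an unadjusted t-test for outcomes that have a baseline value.

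The size is conditional. If caliper matching reached the arm comparison, about 41-46% of patients would be lost at 0.2 SD and none without a caliper. The gain from baseline adjustment depends on a correlation that the documents do not give: a half-width 12% narrower at r = 0.5, and 2% wider at r = 0. Covariates, caliper and correlations are all assumptions.

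This should be fixed before data are seen, but it does not stop the trial. A reader might extend the point to the choice of primary visit, the overlap of scan windows or a dichotomised ultrasound endpoint. Those are separate matters; they do not follow from the adjustment clause, and dichotomising would discard the grades in Table 2.

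**What to change.** Amend the Data Analysis Plan as follows:

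1. State that the t-tests, chi-square tests and any comparative model compare SOC with VB, with randomised patients analysed as assigned and the arm difference reported with a 95% CI. Reconcile this with the sentence that recruits up to 30 subjects whose measurements are valid.
2. For that comparison, delete propensity stratification, propensity matching and the words that leave the choice to the analyst.
3. For each plethysmography outcome, prespecify one linear regression on arm plus the baseline value in place of the unpaired t-test. Do the same for calf circumference only if the baseline and follow-up measures are the same; the baseline list refers to both calves and the follow-up list to the leg.
4. Keep any model of thrombus extent as a separate exploratory analysis, with extent defined from Table 1 or Table 2.

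The cost is wording only: no assessment or patient is added, and the baseline plethysmography is already planned. The analyst loses flexibility, and power for a 1-SD effect falls by about 2 points (75% to 73%) if the baseline value is not prognostic.

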## **Endpoints**

### **Primary:**

Early resolution of the DVT±PE as measured by the ultrasound. Partial recanalization will be defined by normal or diminished flow with distal augmentation and partial incompressibility of the vein (>50% or <50%). Complete recanalization will be defined by spontaneous phasic flow and a completely compressible vein.

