### **Study Rationale Innovation and significance:**

Warming of the lower extremity enhances blood flow in the treatment of superficial vein thrombosis and has been well established. However, the effect of vascular boot warming plus standard anticoagulation on deep venous disease progression is unknown and may prove to reduce DVT with standard anticoagulation more effectively and quicker with reduced risk for PTS. To date, there is no randomized control study evaluating the effect of vascular boot warming plus standard anticoagulation in venous insufficiency. We hypothesize that the combination of vascular boot warming and standard anticoagulation will result in improvement in calf muscle pump function, thus improvement in venous physiology and quicker resolution of DVT and associated clinical symptomatology of post thrombotic syndrome. Ultrasonography with shear wave elastography imaging is a novel ultrasound technology that potentially can quantify and assess thrombosis age, evolution of thrombosis, and risk of detachment. These evaluations can be readily performed in the patient's examination room on a single ultrasound system. The overall anticipated results of our research proposal are to demonstrate that: 1) DVT may resolve more effectively with a vascular boot through warming evaluated by standard 2-D ultrasonography with compression (standard therapy); 2) shear wave elastography is a feasible diagnostic tool in those with lower extremity thrombosis; 3) shear wave elastography can provide a more accurate and reliable method to assess the age of thrombosis and better quantification of thrombosis resolution while assessing the natural history, progression, and risk of detachment; 4) this technology can readily be incorporated into the daily workflow to improve diagnostic and prognostic value for detection of DVT and resolution [It has been estimated that the average image acquisition time to be added to a standard ultrasound study is minimal (7-10 minutes for shear wave elastography imaging) 5) these techniques can improve prediction of complications among those with DVT and; 6) these techniques can help decrease the number of age indeterminate thrombus that may result in unnecessary treatment with anticoagulation and its associated risks.

**Subject Information** – charts, records, images, or specimens are considered ‘subjects’

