#### Baseline studies will include:

- (1) Venous plethysmography: (ejection fraction, VFR, PDR T90, EDV T90, MV, F1.0).
- (2) Lower Extremity Ultrasound: DVT (thrombus) evaluation with 2-D ultrasonography (standard) and shear wave elastography (done within 1 day of baseline clinical ultrasonography).
- (3) Other relevant clinical information (such as height, weight, BMI, bilateral calf circumference, edema, leg pain, ulcerations, previous LE surgery, use of compression stockings, and any current set exercise program). Demographical data, common vascular risk factors (including tobacco use, coronary and peripheral arterial occlusive disease, diabetes, hypercholesterolemia, and hypertension) and the treatment information, will be obtained from chart review via ACE database and Synthesis. All data will be entered and stored in RedCap research tool.
- (4) Anatomic distribution of thrombi at initial examination will be documented as single segment and/or multi-segment(s) involved. The segments will be label as: external iliac vein (EIV), only if clot extends above the common femoral vein; common femoral vein (CFV); femoral vein (FV) (upper, middle, lower); deep femoral vein (DFV); popliteal vein (PV); posterior tibial vein (PTV); gastrocnemius (G-calf); peroneal vein-calf (PV-calf); soleal vein-calf (SV-calf) (see Table 1).

Table 1.0

Site	Anatomic Distribution of Thrombi			
	Initial	3 days	10 days	3 months
Single Segments				
External Iliac (EIV); if evaluated				
Common femoral (CFV)				
Femoral- Upper (FV)				
Femoral - Middle				

Femoral - Lower				
Deep Femoral (DFV)				
Popliteal (PV)				
Posterior Tibial (PT-calf)				
Gastrocnemius (G-calf)				
Peroneal (P-calf)				
Soleal (S-calf)				
Total				
Multisegment				
EIV- CFV				
EIV- CFV-FV				
EIV- CFV-FV-PV				
EIV- CFV-FV-PV-calf				
CFV-FV				
CFV-FV-PV				
CFV-FV-PV-calf				
FV-PV				
FV-PV-calf				
Total				

Patient will then be randomized to vascular boot plus standard anticoagulation program or standard anticoagulation using the randomizer built into RedCap.

**Standard of Care (SOC) Group (no vascular boot utilized)**: Patients will receive standard anticoagulation (determined at discretion of the treating provider), baseline studies, and follow up at the end of treatment (3months).

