**Ultrasound Measurements and Criteria:**

The criteria for complete occlusion (occlusive) were absence of flow with distal augmentation and incompressibility of the vein. Minimal clot will be defined by wall thickening, webbing, etc. Partial recanalization will be defined by >50% or <50% normal or diminished flow with distal augmentation and partial incompressibility of the vein. Complete recanalization (resolved or no clot) will be defined by spontaneous phasic flow and a completely compressible vein and no residual clot (see Table 2).

Table 2.0

Site	No Residual Clot	Minimal Clot (wall thickening, webbing, etc)	Recanalized >50%	Recanalized <50%	Near Occlusive	No Change	Worse Or Extension
External Iliac (EIV); if evaluated							

Common femoral (CFV)							
Femoral- Upper (FV)							
Femoral - Middle							
Femoral - Lower							
Deep femoral (DFV)							
Popliteal (PV)							
Posterior tibial (PT-calf)							
Gastrocnemius (G-calf)							
Peroneal (P-calf)							
Soleal (S-calf)							
Total							

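### The primary endpoint grades the leg vein alone: a vein emptied by embolization gets the best grade, and no rule counts a new PE, or extension at another site, against resolution

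*Combined protocol and SAP*

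**What the plan says.** The Endpoints section gives the primary endpoint as "Early resolution of the DVT±PE as measured by the ultrasound" and then defines the top outcome: "Complete recanalization will be defined by spontaneous phasic flow and a completely compressible vein". The Ultrasound Measurements and Criteria section has a longer version: "Complete recanalization (resolved or no clot) will be defined by spontaneous phasic flow and a completely compressible vein and no residual clot". Table 2 in that section grades 11 venous sites one by one. Its columns run from no residual clot to "Worse Or Extension".

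Table 1, under the baseline studies, maps the thrombosed segments at the initial scan, 3 days, 10 days and 3 months. The external iliac vein is labelled "only if clot extends above the common femoral vein".

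The follow-up data section schedules ultrasound of the affected leg at 3 days, 10 days and 3 months, and no chest imaging. CT is named only under Subject population, as the means of diagnosing PE at entry. Study Procedure plans chart review: "Medical charts will be abstracted for clinical, laboratory, medications, imaging and pathologic findings".

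Safety of the boot is the first secondary objective, but neither the primary nor the secondary endpoint list contains a safety outcome. The study rationale mentions "assessing the natural history, progression, and risk of detachment" among the things elastography may help with.

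**The concern.** The endpoint's name covers the lung, but its instrument sees only the leg. Clot that dissolves in place and clot that detaches both leave an open, compressible vein with nothing in it. The definition cannot tell them apart, and no other rule separates them. A harm could therefore register as the best efficacy result.

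A related gap concerns extension. Grades are given per site, and the plan has no rule for turning up to 11 grades into one result for the patient. A patient whose popliteal vein clears while clot extends elsewhere is recorded accurately in Table 2, but whether that patient has resolved is left open.

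What is at stake is the direction of the main result. The hypothesis is that the boot is both safe and effective, and an efficacy endpoint that can improve because of a harm cannot support both parts.

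**Working it through.** **Step 1. Apply the written definitions to three patients.**

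| What happened | Endpoints definition (flow, compressible) | Ultrasound section definition (adds no residual clot) | Rule that changes the result |
|---|---|---|---|
| Clot dissolves in place | met | met | none needed |
| Clot detaches, new PE | met | met | none found |
| One vein clears, clot extends at another listed site | met for the cleared vein | met if read per vein; not met if read for the whole leg | the other site is graded "Worse Or Extension", but no rule says this overrides the cleared vein |

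The second row follows directly from the text. The third row is indeterminate: the text does not say whether the vein or the leg is the unit. The two definitions also differ from each other, because only the ultrasound section requires that no clot remains.

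**Step 2. Look for a rule elsewhere.** The endpoint lists, the follow-up schedule, Study Procedure and Statistical Considerations contain no scheduled PE assessment after entry and no statement that a new PE is a non-success. They also give no unit of analysis, no visit for early resolution, and no rule for combining segments. Clot above the external iliac vein has no row in Table 2.

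**Step 3. Size.** The plan has no power calculation or event rate to reproduce. It states 30 patients, 15 per arm, and says the number was not calculated. If the endpoint is analysed per patient (an assumption):

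- one reclassified patient: 1/15 = 6.7 percentage points of that arm
- two in the same arm: 2/15 = 13.3 points
- one in each arm: the difference between arms does not change

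**Step 4. Illustration on assumed counts.** The Background cites a study in which over 40% of thrombosed segments had cleared within 3 months. Using 40% as a per-patient control rate is an assumption; it gives 6/15. Take 12/15 for the boot arm, also assumed. The plan compares frequencies by chi-square, two-sided at 0.05. Without continuity correction, χ² = 30(ad − bc)² / (15 × 15 × successes × failures).

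| Boot successes recounted as failures | Boot vs control | χ² | p | Fisher p |
|---|---|---|---|---|
| 0 | 12/15 vs 6/15 | 30 × 90² / (225 × 18 × 12) = 5.00 | 0.025 | 0.060 |
| 1 | 11/15 vs 6/15 | 30 × 75² / (225 × 17 × 13) = 3.39 | 0.065 | 0.139 |
| 2 | 10/15 vs 6/15 | 30 × 60² / (225 × 16 × 14) = 2.14 | 0.143 | 0.272 |

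On these counts one patient moves the planned test across 0.05. This shows how sensitive an arm of 15 is. It does not estimate how often the event would occur.

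**The case against.** The strongest case on the other side has four parts.

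- **Extension is not ignored.** Table 2 has a worsening or extension grade for every listed site and Table 1 re-maps the segments at each visit. In a segment-level analysis the extension counts as worsening. If absence of residual clot is read for the whole leg, the patient is excluded from complete recanalization. This stands. A reader might infer that the plan counts extension as success, but the documents contain no patient-level success rule from which that would follow. What remains is a gap.
- **Nothing links the boot to detachment.** A reader might infer that warming dislodges fresh clot and so biases the trial towards the boot. The documents do not support this. Detachment is mentioned only as something elastography might assess, and the entry criterion limits time since diagnosis, not clot age, which the Background says cannot be determined accurately. Both arms receive anticoagulation, so without a boot effect the misgrading favours neither arm systematically. This also stands, but the endpoint is still unable to reveal such an effect if there were one.
- **This is a pilot.** The form notes that pilots need no endpoints. The plan nevertheless states one and tests at 0.05, so its direction should be interpretable.
- **A PE rule is imperfect.** No baseline chest imaging is listed for all patients, so a PE found later may have been present at entry. Patients know their assignment, so clinically detected PE may be ascertained unequally. Both are real limits on the fix. They do not justify leaving a documented PE without effect on an endpoint that names PE.

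**Conclusion.** The embolization point holds on the text: both definitions would give an embolized clot the best grade, scheduled follow-up imaging cannot see the lung, and no rule or safety endpoint corrects this. The extension point holds only as an omission: extension is recorded by site, but its effect on the patient's result is undefined, so the patient is not ruled out as resolved.

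The size is 6.7 percentage points of an arm per affected patient, provided the endpoint is analysed per patient, which the plan does not say. The number of affected patients and any imbalance between arms cannot be derived from the documents, and the p-values above rest on assumed counts. The change is worth making because it is cheap and settles how such a patient is scored before data are seen.

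**What to change.** In the Endpoints section:

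- Adopt the ultrasound section's definition, including absence of residual clot, so that there is one definition.
- State that a patient is resolved at a visit only if (a) no examined segment has residual clot or a "Worse Or Extension" grade at that visit, and (b) no new, objectively confirmed PE has been documented since randomisation in the chart and imaging abstraction already planned.
- Apply the extension rule visit by visit, without carrying it forward, so that an extension which later clears does not block resolution at 3 months.
- Do not treat a segment that was not examined at day 0, such as a conditionally scanned external iliac vein, as clear at baseline.
- Report the ultrasound-only result as a sensitivity analysis.
- Report new PE and extension by arm as safety outcomes for the first secondary objective.

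The cost is a short text change, a derived variable, and abstraction of PE through the 3-month visit, with no added imaging. The resolution rate may be slightly lower, silent emboli remain undetected, and clinically detected PE may be found unequally between arms because patients know their assignment. The rule changes scoring only, not patient care.
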